Abbreviations: BMI = body mass index; DLQI = Dermatology Life Quality Index; ECG = electrocardiogram; ET = early termination; HEENT = head, eyes, ears, nose, throat; ICF = informed consent form; IGA = Investigator’s Global Assessment; IWRS = interactive web response system; OLE = open-label extension; PK = pharmacokinetic; WOCBP = women of childbearing potential; VIIS = Visual Index for Ichthyosis Severity

- a. Upon signing informed consent and entering the Screening Period, subjects will stop using physical and medical treatments for LI, including balneotherapy, and begin to washout prohibited topical and systemic treatments with designated washout periods, as applicable. Before asking a subject to enter washout, investigators should confirm the subject meets study eligibility criteria, except for LI severity (Inclusion Criterion #3). Washout may be up to 90 days. After completing any necessary Washout Period, subjects must return to the site within 35 days before the Baseline Visit within the 97-day Screening Period to have their LI severity assessed and study eligibility requirements determined. During washout, subjects may continue their standard of care of visible skin (face and scalp) for cosmetic reasons and of extremities (palms/soles) to avoid functional consequences on walking or moving their fingers. In the US/EU, this may include compounded emollients with keratolytics (alpha or beta hydroxyl acids) and/or urea. The investigator should approve and document these standard of care treatments in the electronic case report form (eCRF). If the standard of care treatments of the face and/or palms/soles contain prohibited medications, they must be stopped at the Baseline Visit. Subjects may shower, but not bathe or swim, during the Screening Period.
- b. Day 90 procedures should be conducted for subjects who terminate the study early. If a subject discontinues IP, but continues to attend clinic visits, Day 90 will occur as scheduled. Day 90 will be the first visit of the OLE for subjects who choose to continue. Subjects who decide to continue into the OLE will have the following additional procedures: 1) sign informed consent; 2) will be weighed; 3) will be instructed on study drug application; 4) will be given new diaries, and 5) will be provided with study drug.
- c. A Follow-up telephone call will be made within 14 days after Day 90 to subjects who choose not to continue into the OLE to assess any ongoing adverse events.

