- o. Study staff will apply initial dose of study drug in the clinic after Baseline measurements, and the amount of study drug used will be measured (i.e., 36-g tube will be measured before and after application to determine amount used).
- p. Study drug provided in 50-g tubes (maximum single application is 36 g). Measure study drug kits (tubes and box, but not leaflets) before dispensing; subjects must record days/times of study drug application in the diaries and any areas of skin not treated, e.g., due to local reactions. Dispense enough additional study drug until next visit (except at Day 90, unless subject consents to continue into OLE).

- q. Confirm study drug compliance by weighing the studykits (tubes and boxes, but not leaflets) and reviewing diary.

Table 2: Schedule of Events for Open-label Extension

	Open-label Treatment Period ^a						Follow-up
	Telephone Visit (Day 97) ^a	Day 104 ± 5 days	Day 120 ± 7 days	Telephone Visit (Day 134)	Day 150 ± 7 days	Day 180 ± 7 days/ET	Day 194 or 14 days after End of Open-label Treatment
Visit		7 ^a	8 ^a		9 ^a	10 ^a	11 ^a
Informed consent ^b							
Physical examination ^c						X	X
Vital signs (blood pressure and pulse)			X	X	X	X	X
Record IGA ^d		X	X		X	X	X
VIIS ^e assessment		X	X		X	X	X
Roughness assessment ^f		X	X		X	X	X
Palm/sole assessment		X	X		X	X	X
Palm/sole fissuring assessment		X	X		X	X	X
Ectropion score		X	X		X	X	X
Clinical laboratory tests (hematology, chemistry, urinalysis) ^g			X			X	
Pregnancy test for female subjects (urine) ^h			X		X	X	X
Coagulation panel			X			X	
12-lead ECG			X			X	
PK blood sample collection ⁱ			X			X	
Application instructions, advice on emollient and sunscreen use ^j	X	X	X	X			
Dispense study drug and diaries ^k		X	X		X		
Concomitant medications	X	X	X	X	X	X	X

	Open-label Treatment Period ^a						Follow-up
	Telephone Visit (Day 97) ^a	Day 104 ± 5 days	Day 120 ± 7 days	Telephone Visit (Day 134)	Day 150 ± 7 days	Day 180 ± 7 days/ET	Day 194 or 14 days after End of Open-label Treatment
Visit		7^a	8^a		9^a	10^a	11^a
Tolerability assessment		X	X		X	X	
Adverse events (and review diaries)	X	X	X	X	X	X	X
Collect all used/unused study drug ¹		X	X		X	X	

Abbreviations: ECG = electrocardiogram; ET = early termination; HEENT = head, eyes, ears, nose, throat; ICF = informed consent form; IGA = Investigator's Global Assessment; PK = pharmacokinetic; OLE = open-label extension; VIIS = Visual Index for Ichthyosis Severity; WOCBP = women of childbearing potential

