- Although it is preferable to conduct all necessary study assessments in person (on -site visits), this may not be possible as a result of COVID-19-related travel restrictions. To ensure the safety of subjects, investigators, and site staff, Visits 7-11 and unscheduled visits may be conducted remotely.
- Subjects will sign the OLE ICF at the Double-blind Day 90 Visit. All efficacy assessments, safety/tolerability assessments, including clinical laboratory testing and PK from Day 90 will be carried over for the OLE and will not be repeated.
- Limited physical examination to include HEENT, cardiorespiratory, abdomen, range of motion.
- IGA: 0 = clear; 1 = almost clear; 2 = mild; 3 = moderate; 4 = severe
- VIIS scale for each body area: chest/abdomen, back, legs, and arms, for a possible overall score = 16.
- Roughness (0-4 scale); fissuring assessment on palms/soles: present/absent/number/pain (0-3 scale).
- Subjects must be fasting (at least 8 hours) for clinical chemistry testing, but not for PK only blood draws.
- Subjects who are premenstrual at Screening but begin menses during the course of the study should follow the pregnancy testing schedule for WOCBP correlating to the visit menses began.
- Samples for PK will be drawn from all subjects at Day 120 and Day 180. Visits for PK must occur at least 24 hours after the last application of the IP to avoid contamination of the blood samples with any IP that may have remained in the skin after the last application.
- Subjects must record days/times of study drug application in the diaries and any areas of skin not treated (e.g., due to local reactions).
- All subjects in the OLE will receive trifarotene 200 µg/g. Study drug provided in 50-g tubes (maximum single application is 36 g). Measure study drug tubes before dispensing. Dispense enough additional study drug until the next visit (except at Day 180).
- Confirm study drug compliance by weighing the study kits (tubes and boxes, but not leaflets) dispensed and returned and reviewing diary.

4. Statistical Analysis and Reporting

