6.1.7. Derived Variables

- IGA average score = in protocol version 1.0, IGA was assessed by body area (chest/abdomen, back, arms, and legs). Under protocol version 2.0, this was changed to a global (overall) assessment. For comparability, the average of the body area IGA results will be taken to yield one score for subjects enrolled under protocol version 1.0. Scores will range from 0 to 4. Higher scores indicate worse disease.
- VIIS total score = sum of the individual body area scaling scores, with a range of 0 to 16. Each individual item is scored on a scale of 0-4, where 0 = normal skin; no perceptible scale or smoothening and 4 = confluent, primarily large, thick scales. Higher scores indicate worse scaling.
- Ectropion total score = sum of the 8 individual item scores (lateral apposition, medial apposition, scleral show, conjunctival show, excess tear film, redness of the eye, round canthus, punctum lacrimale), with a range of 0 to 8. Each individual item is scored 0

(nonaffected/no/invisible), 0.5 (≤ 1 mm/emerging), or 1 (affected/yes/visible). Higher scores indicates worse ectropion.

- DLQI total score = sum of the 10 individual item scores, with a range of 0 to 30. Higher scores indicate poorer quality of life.
- CDLQI total score = sum of the 10 individual item scores, with a range of 0 to 30. Higher scores indicate poorer quality of life.
- Number of doses taken = total number of tubes returned – total number of tubes returned unused
- Number of weeks on study = (last day on study – treatment start date + 1) / 7
- Number of expected doses = 2 * number of weeks on study
- Total weight used = total weight of tubes dispensed (grams) – total weight of tubes returned (grams)
- Initial application amount used = tube weight before drug application (grams) – tube weight after drug application (grams), as collected on the initial study drug application CRF
- Compliance by tube weight = total weight used / total weight of tubes dispensed * 100%
- Compliance by number of doses = number of doses taken / number of expected doses * 100%
- Change from baseline = value at current time point – value at baseline.
- TEAE = An AE is defined as treatment emergent if the onset or worsening is at the time of or following the start of the first application of study drug (trifarotene or vehicle) through the Follow-up Visit or Early Termination Visit, whichever occurs first..

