Note: Percentages are n/Number of subjects in the Safety population within actual treatment group and overall*100. Medications were coded using WHO-DDE version March 2019. Prior medications are all medications that were started before the first dose of study drug. Medications are displayed by descending frequency of ATC Level 4 classification, by PT within ATC, and then alphabetically by PT, based on the overall column. Subjects were counted only once for each ATC and PT.

SOURCE: Listing 16.2.9.5

Programming note: ATC & PT text should be in title case in table, as shown in the shell.

Table 14.1.5.1
Summary of Drug Accountability (Drug Returned and Dispensed)
Safety Population

Visit Parameter Statistic	Trifarotene cream HE1 100 ug/g (N=XX)	Trifarotene cream HE1 200 ug/g (N=XX)	Vehicle (N=XX)	Overall (N=XX)
Baseline [1]				
Total Weight of Tubes Dispensed (g)				
n	XX	XX	XX	XX
Mean (SD)	XX.X (XX.XX)	XX.X (XX.XX)	XX.X (XX.XX)	XX.X (XX.XX)
Median	XX.X	XX.X	XX.X	XX.X
Min, Max	XX, XX	XX, XX	XX, XX	XX, XX
Day 14				
Total Weight of Tubes Dispensed (g)				
n	XX	XX	XX	XX
Mean (SD)	XX.X (XX.XX)	XX.X (XX.XX)	XX.X (XX.XX)	XX.X (XX.XX)
Median	XX.X	XX.X	XX.X	XX.X
Min, Max	XX, XX	XX, XX	XX, XX	XX, XX
Total Number of Tubes Returned				
n	XX	XX	XX	XX
Mean (SD)	XX.X (XX.XX)	XX.X (XX.XX)	XX.X (XX.XX)	XX.X (XX.XX)
Median	XX.X	XX.X	XX.X	XX.X
Min, Max	XX, XX	XX, XX	XX, XX	XX, XX

Abbreviation: OLE = open label extension. SD = standard deviation.

Note: Subjects are summarized by actual treatment group. Subjects were randomized to either Trifarotene cream HE1 100 ug/g, Trifarotene cream HE1 200 ug/g, or vehicle in the Double-blind period. All subjects received Trifarotene cream HE1 200 ug/g in the OLE.

[1] Baseline is defined as the last non-missing assessment recorded prior to the first dose of treatment in the Double-blind Period.

SOURCE: Listings 16.2.5.1, 16.2.5.2, 16.2.5.3

Table 14.1.5.1 (cont.)
Summary of Drug Accountability (Drug Returned and Dispensed)
Safety Population

Visit Parameter Statistic	Trifarotene cream HE1 100 ug/g (N=XX)	Trifarotene cream HE1 200 ug/g (N=XX)	Vehicle (N=XX)	Overall (N=XX)
Day 14				
Total Number of Tubes Returned Unused				
n	XX	XX	XX	XX
Mean (SD)	XX.X (XX.XX)	XX.X (XX.XX)	XX.X (XX.XX)	XX.X (XX.XX)
Median	XX.X	XX.X	XX.X	XX.X
Min, Max	XX, XX	XX, XX	XX, XX	XX, XX
Total Weight of Tubes Returned (g)				
n	XX	XX	XX	XX
Mean (SD)	XX.X (XX.XX)	XX.X (XX.XX)	XX.X (XX.XX)	XX.X (XX.XX)
Median	XX.X	XX.X	XX.X	XX.X

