Min, Max	XX, XX	XX, XX	XX, XX	XX, XX

Abbreviation: OLE = open label extension. SD = standard deviation.

Note: Subjects are summarized by actual treatment group. Subjects were randomized to either Trifarotene cream HE1 100 ug/g, Trifarotene cream HE1 200 ug/g, or vehicle in the Double-blind period. All subjects received Trifarotene cream HE1 200 ug/g in the OLE.

SOURCE: Listings 16.2.5.1, 16.2.5.2, 16.2.5.3

Programming note: Continue for Day 30, Day 60, and Day 90.

Table 14.1.5.2
Summary of Drug Accountability (Drug Returned and Dispensed)
OLE Safety Population

Same shell as Table 14.1.5.1

Programming note: Only include one column for Trifarotene cream HE1 200 ug/g.

Continue for Day 104, Day 120, Day 150 and Day 180.

Update Note: to read "Note: Subjects are summarized by treatment group. All subjects received Trifarotene cream HE1 200 ug/g in the OLE."

Table 14.1.5.3
Summary of Treatment Exposure and Compliance
Safety Population

Variable Statistic or Category	Trifarotene cream HE1 100 ug/g (N=XX)	Trifarotene cream HE1 200 ug/g (N=XX)	Vehicle (N=XX)	Overall (N=XX)
Compliance by Tube Weight (%) [1]				
n	XX	XX	XX	XX
Mean (SD)	XX.X (XX.XX)	XX.X (XX.XX)	XX.X (XX.XX)	XX.X (XX.XX)
Median	XX.X	XX.X	XX.X	XX.X
Min, Max	XX, XX	XX, XX	XX, XX	XX, XX
Compliant	XX (XX.X%)	XX (XX.X%)	XX (XX.X%)	XX (XX.X%)
Not Compliant	XX (XX.X%)	XX (XX.X%)	XX (XX.X%)	XX (XX.X%)
Compliance by Number of Doses (%) [2]				
n	XX	XX	XX	XX
Mean (SD)	XX.X (XX.XX)	XX.X (XX.XX)	XX.X (XX.XX)	XX.X (XX.XX)
Median	XX.X	XX.X	XX.X	XX.X
Min, Max	XX, XX	XX, XX	XX, XX	XX, XX
Compliant	XX (XX.X%)	XX (XX.X%)	XX (XX.X%)	XX (XX.X%)
Not Compliant	XX (XX.X%)	XX (XX.X%)	XX (XX.X%)	XX (XX.X%)

Abbreviation: SD = standard deviation.

Note: Percentages are n/Number of subjects in the Safety population within actual treatment group and overall*100. A subject is compliant with study product if he or she takes at least 80%-120% of the scheduled doses as assessed by diary entries, supplemented by tube weight.

[1] Compliance by tube weight = total weight used / total weight of tubes dispensed *100%, where total weight used = total weight of tubes dispensed (grams) – total weight of tubes returned (grams)

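### The accountability shells book the open-label cream dispensed at Day 90 in the double-blind table, including under vehicle, and give it no dispensing row in the OLE table

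*SAP*

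**What the plan says.** **Double-blind table.** In SAP 14.2, Table 14.1.5.1 covers the Safety population in columns for 100 µg/g, 200 µg/g, vehicle and overall. Its note reads "Note: Subjects are summarized by actual treatment group". The Baseline block has a dispensed-weight row only. The Day 14 block has "Total Weight of Tubes Dispensed (g") together with tubes returned, tubes returned unused and weight returned. The shell then instructs: "Programming note: Continue for Day 30, Day 60, and Day 90".

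**OLE table.** Table 14.1.5.2 reuses that shell with a single 200 µg/g column and the instruction "Continue for Day 104, Day 120, Day 150 and Day 180".

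**What is dispensed at Day 90.** Section 3.7, Table 1, note p: "Dispense enough additional study drug until next visit (except at Day 90, unless subject consents to continue into OLE". Note b: "Day 90 will be the first visit of the OLE for subjects who choose to continue". The notes to Table 2 add: "All subjects in the OLE will receive trifarotene 200 µg/g".

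**Derivations.** Section 6.1.7: "Total weight used = total weight of tubes dispensed (grams) – total weight of tubes returned (grams"). Tube-weight compliance is that quantity divided by the weight dispensed. Neither 6.1.7, 7.4 nor the shells of Tables 14.1.5.3 and 14.1.5.4 say how dispensed and returned weights are split between the two periods.

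**The concern.** Day 90 is both the last double-blind visit and the first OLE visit. What is handed back there is double-blind cream; what is handed out is open-label active cream. The shells treat the visit as wholly double-blind. A programmer following them would report active cream as dispensed to the vehicle group, and would report the first OLE supply as returned without ever having been dispensed.

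What is at stake is the readability of the accountability tables and, if period totals are built the same way, the reported weight used and tube-weight compliance. The staged reporting (sections 3.6 and 4.2) makes a split by visit a natural choice: the double-blind data are locked and analysed first, when the Day 90 dispensing is on file as a Visit 6 record and its return belongs to Visit 7.

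**Working it through.** **1. Display.** This part needs no assumption.

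| Event | Supply | Table that shows it |
|---|---|---|
| Dispensed at Day 60, returned at Day 90 | Double-blind | 14.1.5.1, both ends |
| Dispensed at Day 90 | Open-label 200 µg/g | 14.1.5.1, by double-blind arm |
| Returned at Day 104 (first OLE collection in Table 2) | The same open-label tubes | 14.1.5.2 |

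The two ends of one supply therefore fall in different tables. If Table 14.1.5.2 also keeps the Baseline block of the reused shell, that block is tied by its footnote to the time before the first double-blind dose. It would then put Day 1 blinded supply, vehicle included, in the 200 µg/g column.

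**2. Totals, if they follow the visits each table lists.** The SAP does not give the number of tubes dispensed, so the following are assumptions:
- One 50 g tube per application, twice weekly. By interval this is 2×14/7 = 4, 2×16/7 = 4.6 (taken as 5) and 2×30/7 = 8.6 (taken as 9) twice: 4 + 5 + 9 + 9 = 27 tubes per period.
- All tubes returned, tare ignored.
- Day 90 supply of 4 tubes = 200 g.
- Baseline block not carried into the OLE table.

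With x grams per application, returned weight per period is 27 × (50 − x). Dispensed weight is 27 × 50 = 1350 g if split correctly, (27 + 4) × 50 = 1550 g as listed for the double-blind period, and (27 − 4) × 50 = 1150 g as listed for the OLE.

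| x | Returned | Correct use | Double-blind as listed | OLE as listed |
|---|---|---|---|---|
| 36 g | 378 g | 972 g (72.0%) | 1172 g (75.6%) | 772 g (67.1%) |
| 20 g | 810 g | 540 g (40.0%) | 740 g (47.7%) | 340 g (29.6%) |

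Percentages are used ÷ dispensed. The shift in use is 200/972 = 20.6% at 36 g and 200/540 = 37.0% at 20 g.

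If 6 tubes were given to cover the +5-day window (2×19/7 = 5.4), the 36 g figures become 1272/1650 = 77.1% and 672/1050 = 64.0%.

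**3. With the Baseline block carried over.** If Day 1 supply is also 4 tubes, the OLE table shows 4 + 23 = 27 tubes dispensed and the total comes out at 972 g and 72.0%. The number is right, but only because blinded Day 1 cream stands in for the open-label supply.

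**4. Compliance call (80% to 120%, section 7.4).** Every value above is below 80%, correct or not. At 36 g, reaching 80% needs (972 + 50k)/(1350 + 50k) ≥ 0.8, so 10k ≥ 108 and k = 11 tubes at Day 90, far more than needed to reach Day 104.

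**5. Dose count.** In 6.1.7 this is tubes returned minus tubes returned unused, so Day 90 dispensing does not enter it. The footnote to Table 14.1.5.3 starts from tubes dispensed and would be affected, but that disagreement with 6.1.7 is a separate matter.

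**The case against.** The strongest reply is that Tables 14.1.5.1 and 14.1.5.2 hold only per-visit rows. Neither has a used row or a cumulative total, so a Day 90 figure labelled Day 90 distorts no other row. Weight used appears only through 6.1.7 and Tables 14.1.5.3 and 14.1.5.4, and the SAP never says that those totals are summed over the visits the accountability tables list. This stands: a reader might infer that weight used and compliance are certain to be wrong, but the document supports that only conditionally.

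The OLE shortfall is also uncertain, because the inherited Baseline block could offset it in the arithmetic. That stands as well, although the block would bring in the wrong cream.

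A reader might go further and infer a spurious difference between arms, since only OLE entrants are affected. With 90% entry in one arm and 70% in another, a 200 g supply would give 0.2 × 200 = 40 g. Those entry rates are invented for the illustration, and nothing in the SAP suggests unequal entry. Nor is a change in per-protocol membership shown: section 7.4 judges compliance on doses taken, with tube weight as a supplement, and no worked example crosses 80%.

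Finally, Listing 16.2.5.2 carries kit IDs and visit-level weights, so a careful programmer could assign each supply correctly. That makes the repair easy, but no instruction in the SAP requires it.

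**Conclusion.** The display fault holds on the SAP's own text. Open-label 200 µg/g cream dispensed at Day 90 is shown by double-blind arm, including vehicle and 100 µg/g, and the OLE table has no row for its dispensing.

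The effect on totals is conditional. If the period totals follow the same visits, double-blind use for OLE entrants is overstated by the Day 90 supply. OLE use is understated by the same amount if the Baseline block is not carried over. The gram and percentage figures are illustrations resting on the assumed tube numbers, full return and no tare; weighing kits with their boxes would change the percentages.

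Severity is minor. Only descriptive accountability and compliance tables are touched. The 6.1.7 dose count and the ITT primary analysis are not affected.

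**What to change.** 1. Table 14.1.5.1: limit the Day 90 block to the return rows.
2. Table 14.1.5.2: replace the inherited Baseline block with a dispensing row labelled *Day 90 (OLE supply)*, followed by Days 104, 120, 150 and 180. The Baseline block has to go; adding the Day 90 row while keeping it would count two initial supplies.
3. Section 6.1.7: state that dispensed and returned weights belong to the period of the kit dispensed, namely Baseline to Day 60 for the Double-blind Period and Day 90 to Day 150 for the OLE, with returns matched through the kit IDs in Listing 16.2.5.2.

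The cost is two programming notes and one derivation line. No new data are needed.
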